New version/date: Version 4.0, 05 Nov 2015 (per Amendment 02)

| Change | Rationale | Affected Protocol Sections |
|--|---|---|
| regarding scope of Exclusion Criterion No. 34 which excludes subjects with hypopigmentation conditions. | for the sites. | 
 ○ Exclusion Criteria ● Section 9.3.2 |
| Revised number of clinical sites from 30 to 40 | For feasibility purposes | 
 ● Synopsis – ○ Sites ● Section 6 ● Section 9.1 ● Section 9.3 |
| Relaxed the requirement for the cognitive assessments at Screening Visit 1 to be conducted in a certain order and revised the recommended order in which the assessments could be conducted. | To provide the sites with greater operational flexibility. | 
 ● Section 9.1.1 ● Figure 2 ● Section 9.5.1.3.1 ● Section 9.5.2 ● Table 6 |
| Clarify the duration for which the Safety magnetic resonance imaging (MRI) scan, the amyloid PET scan and the lumbar puncture (LP) collected CSF conducted at Screening are considered valid. | To provide sites with greater operational flexibility, particularly for re-screening of screen fail subjects. | 
 ● Section 9.1.1 |
| Clarify that for subjects meeting criteria for weekly monitoring of lymphocyte subsets, these can be accommodated within the scheduled clinic visits during the early stages of the treatment period of the study. | To provide operational clarity to the sites. | 
 ● Synopsis – ○ Exclusion Criteria ● Section 9.3.2 ● Section 9.3.3 ● Section 9.5.1.5.3 |
| Added the requirement for complete blood counts (CBC) with differentials to be performed whenever repeat or unscheduled flow cytometry tests are performed. | Such that CBC data are available at all times when flow cytometry data is available. | 
 ● Section 9.3.3 ● Table 1 ● Section 9.5.2 ● Table 6 ● Table 7 |

Revisions to Version 3.0

New version/date: Version 4.0, 05 Nov 2015 (per Amendment 02)

| Change | Rationale | Affected Protocol Sections |
|---|---|--|
| Added 30 day window to the duration of the pre-treatment period if required for medical or operational reasons. | To provide the sites with greater operational flexibility. | 
 • Synopsis – 
 ○ Study Design ○ Duration of Treatment • Section 9.1 • Figure 1 • Section 9.1.1 • Section 9.1.1.2 • Section 9.5.2 • Table 6 |
| Clarified the timing of the start of the Randomization Phase | Clarification | 
 • Section 9.1.1 • Section 9.1.2 • Section 9.5.2 • Table 6 • Table 7 |
| Increased number of MCI/Prodromal or mild to moderate AD subjects screened for entry into the study | To reflect the higher screen failure rate than originally anticipated | 
 • Synopsis – 
 ○ Number of Subjects |
| Removal of CD127 cell surface markers | FoxP3 is the most accepted marker to measure T regulatory cells and additional assessment of CD127 is not required. | 
 • Section 9.5.1.5.3 • Table 4 • Section 9.5.2.1 |
| Made the clinical biochemistry, urinalysis, CBC, lymphocyte subsets, and immunoglobulin tests mandatory at Visit 20, regardless of clinical significance at Visit 19. | For more comprehensive safety data at the second follow-up visit. | 
 • Section 9.5.2 • Table 7 |
| Corrected reference to Exclusion Criterion No. 20 (and not to Exclusion #19) in footnote to Table 6 and Table 7 regarding timing of Visit 3 in relation to Visit 2. | Correction | 
 • Section 9.5.2 • Table 6 • Table 7 |
| Revised details regarding prohibited antiplatelet drugs | To distinguish between those subjects who consent to CSF sample collection and those who do not | 
 • Appendix 2, Listing 2 |

Revisions to Version 2.0

New version/date: Version 3.0, 28 May 2015 (per Amendment 01)

| Change | Rationale | Affected Protocol Sections |
|--|--|---|
| 
Revised inclusion to allow for enrollment of mild to moderate AD subjects in Stage A and expand the Stage B mild AD cohort to also include moderate AD subjects
 | 
To collect safety data in a wider range of AD patients.
 | 
 • Title Page • Synopsis – 
 ○ Objectives ○ Study Design ○ Number of Subjects ○ Inclusion/Exclusion Criteria ○ Study Treatments ○ Efficacy Assessments ○ Study Endpoints ○ Efficacy Analyses ○ Interim Analyses ○ Adaptive Randomization ○ Sample Size • Section 5.3 • Section 7 • Section 8 (and all subsections) • Section 9.1 • Section 9.1.1 • Figure 1 • Section 9.2.1 • Section 9.2.2 • Section 9.2.3 • Section 9.2.4.3 • Section 9.2.4.4 • Section 9.3 • Section 9.3.1 • Section 9.3.2 • Section 9.4.1 • Section 9.4.3 • Section 9.4.4 • Section 9.5.1.3.1 • Section 9.7.1.1.2 • Section 9.7.1.1.3 • Section 9.7.1.4 • Section 9.7.1.6 • Section 9.7.1.6.2 • Section 9.7.1.6.3 • Section 9.7.1.8.2 • Section 9.7.3 • Section 9.7.4 |

Revisions to Version 2.0

New version/date: Version 3.0, 28 May 2015 (per Amendment 01)

| Change | Rationale | Affected Protocol Sections |
|---|---|---|
| Revised inclusion criteria for MMSE to ≥ 16 from ≥ 20 | The MMSE score is used as a cut-off for the most impaired subject that would be eligible for the study. Lowering the MMSE inclusion from ≥ 20 to ≥ 16 is consistent with expanding the Mild AD cohort to a Mild to Moderate AD cohort. | 
 • Synopsis – 
 ○ Inclusion/Exclusion Criteria • Section 9.3.1 |
| Revised inclusion criteria for FAQ to ≤ 24 from ≤ 20 | As for the MMSE, the FAQ score is used as a cut-off for the most impaired subject that would be eligible for the study. Revising the FAQ inclusion from ≤ 20 to ≤ 24 is consistent with expanding the Mild AD cohort to a Mild to Moderate AD cohort, and is consistent with an MMSE inclusion of ≥ 16 . | 
 • Synopsis – 
 ○ Inclusion/Exclusion Criteria • Section 9.3.1 |
| Revised exclusion criteria such that small arachnoid cysts are not necessarily exclusionary | Arachnoid cysts are a common finding in otherwise healthy subjects. Small lesions (<1 cm in diameter) are generally not considered clinically significant and if discovered incidentally no long term follow up is routinely required. | 
 • Synopsis – 
 ○ Inclusion/Exclusion Criteria • Section 9.3.2 |
| Revised exclusion criteria for Ig (IgG, IgA, or IgM) to specify that levels below the LLN at Screening or Baseline need not be exclusionary | For subjects with a Screening or Baseline IG level <LLN to be considered for continuation in the study, assessment of clinical significance of the finding will be required. A finding of "not clinically significant" must be agreed between the Investigator and Medical Monitor in order for the subject to continue in the study. | 
 • Synopsis – 
 ○ Inclusion/Exclusion Criteria • Section 9.3.2 |
| Revised text to provide instructions for subject assent and associated consent by a legal representative for subjects who the Investigator considers not to have the capacity to consent themselves | With the expansion of the patient population to include moderately demented subjects it was necessary to provide directions regarding the consenting process for subjects considered to be lacking the | 
 • Section 5.3 |

Revisions to Version 2.0

New version/date: Version 3.0, 28 May 2015 (per Amendment 01)

| Change | Rationale | Affected Protocol Sections |
|--|--|--|
| | capacity to consent themselves. | |
| Revised number of clinical sites to 30 from 25 | For feasibility purposes. | 
 • Synopsis – 
 ○ Sites • Section 6 • Section 9.1 • Section 9.3 |
| Added allowance for Tier 1 and Tier 2 screening assessments to be performed on the same day | Added to provide operational clarity for the sites. | 
 • Section 9.1.1.1 • Table 6 |
| Removed requirements for MRIs to include sequences for resting state functional MRI | This was an error and should not have been included in the original protocol. | 
 • Table 6 • Table 7 |
| Revised text to clarify that on visits where CSF collection takes place, the CSF collection need not take place on the same day as the cognitive testing for that visit | Added to provide operational clarity for the sites. | 
 • Section 9.5.1.4.2 • Table 6 • Table 7 |
| Revised text to clarify that the most important efficacy assessment to keep blinded from safety data is the CDR. | Added to provide operational clarity for the sites. | 
 • Synopsis – 
 ○ Safety Assessments • Section 9.4.6 • Section 9.5.1.5 |
| Revised text to allow PK blood sample and PD blood samples to be taken either shortly before or shortly after the LP on CSF days | Added to provide operational flexibility for the sites. | 
 • Section 9.5.1.4.1 • Section 9.5.1.4.2 • Table 6 • Table 7 |
| Revised Sponsors Grading for Laboratory Values for the following analytes: lymphocytes, neutrophils, albumin, creatinine, phosphate, and potassium serum-high (hyperkalemia) | Corrections made to align with the values for grading used by the central clinical laboratory for this study. | 
 • Appendix 1 |
| Revised details regarding prohibited antiplatelet drugs | Previous version incorrectly referenced a biomarker subgroup. All subjects in this study will need to provide CSF samples. | 
 • Appendix 2; Listing 2 |
| Revised grammar, spelling, etc. | Compliance with current company style guide and for general consistency. | Throughout protocol |

Revisions to Version 1.0

New version/date: Version 2.0, 21 Oct 2014 (revised original protocol)

| Change | Rationale | Affected Protocol Sections |
|--|---|--|
| Revisions to grammar, spelling, etc. | Compliance with current company style guide and for general consistency | 
 • Throughout protocol |
| Revisions made per new company protocol template | Alignment with current Eisai template | 
 • Synopsis – 
 ○ Inclusion/Exclusion Criteria • Section 9.1.2.3 • Section 9.3.1 • Section 9.3.2 • Section 9.5 (related subsections) • Section 9.5.4 • Section 9.5.4.1 • Section 9.5.4.2 • Section 9.5.4.3 |
| Clarified classification of MCI due to AD | Clarification that MCI due to AD population will also be consistent with the research criteria for Prodromal AD in that impaired episodic memory is required and will be tested using a list learning task (the International Shopping List Task) | 
 • Synopsis – 
 ○ Study Design • Section 9.1 |
| Replaced “enroll” with “randomize,” pertaining to subject entry into study | Correction to terminology | 
 • Synopsis – 
 ○ Study Design • Section 9.1 • Section 9.3 |
| Added criterion excluding subjects with hepatic impairment and total bilirubin greater than 1.5×ULN or INR greater than 1.7 at Screening or Baseline. Subjects with Gilbert’s syndrome need not be excluded. | At request of FDA, exclude subjects who have hepatic impairment | 
 • Synopsis – 
 ○ Inclusion/Exclusion Criteria • Abbreviation List • Section 9.3.2 |
| Added coagulation parameters for prothrombin time (PT), partial thromboplastin time (PTT), and International Normalized Ratio (INR) to screening and baseline procedures | Screen for hepatic impairment | 
 • Synopsis – 
 ○ Inclusion/Exclusion Criteria • Abbreviation list • Section 9.3.2 • Table 4 • Table 6 • Table 8 |
| For subjects who discontinue study drug prematurely, conduct efficacy assessments postdose at same time points as subjects who continue in the study. Added FAQ to this set | To facilitate efficacy analyses, which are based on longitudinal modeling for all subjects | 
 • Synopsis – 
 ○ Study Design • Section 9.1.2.2 • Section 9.3.3 • Section 9.5.4.1 |

Revisions to Version 1.0

New version/date: Version 2.0, 21 Oct 2014 (revised original protocol)

| Change | Rationale | Affected Protocol Sections |
|--|--|--|
| of efficacy assessments. | | 
 • Section 9.5.5 • Table 7 |
| Delete diagram of E2609 structure | This display is not needed for the protocol. The Investigator's Brochure has this information. | 
 • Section 9.4.2.1 |
| Additional blood samples to be taken at Visits 19 and 20 | Samples are to be put in storage to allow for assessment of immune status at end of study, as needed. | 
 • Synopsis – 
 ○ Assessments • Table 8 |
| Add subheadings to Section 9.7 describing the primary endpoint analysis, and text clarifying that no multiplicity adjustments will be done to account for the interim analyses | To distinguish clearly the primary analysis and the sensitivity analyses of the primary endpoint | 
 • Synopsis – 
 ○ Efficacy Analyses • Section 9.7.1.6.1 |
| Clarification of PK sampling upon Early Discontinuation | Additional operational details of the timing of the PK sampling at the ED visit provided | 
 • Section 9.5.1.4.1 • Table 7 |
| Clarification of ApoE testing | Clarification that the ApoE genetic testing will be for homozygous or heterozygous E4, versus non-E4 | 
 • Section 9.5.1.4.2 |
| Revision to PK/PD interim analysis text | Confirm that interim PK/PD analysis will be conducted by an independent group | 
 • Section 9.4.6 |
| Addition of text regarding safety signals with E2609 | To provide information on safety-driven dose adjustments | 
 • Synopsis – 
 ○ Study Design • Section 9.1 |
| Addition of PBMC collection/assessment at Baseline, during treatment, and post-treatment | Recent animal studies have shown an effect of E2609 on this model so they will be added to the 202 clinical study as an additional exploratory assessment. | 
 • Synopsis – 
 ○ Safety Assessments • Section 9.2.5 • Section 9.5.1.5 • Table 4 • Table 6 • Table 7 • Table 8 |
| Stipulate that exploratory biomarker analyses may be conducted using blood or CSF samples that may have been drawn for other purposes | To allow more flexibility for possible exploratory biomarker studies associated with study drug or disease, including miRNA and DNA | 
 • Synopsis – 
 ○ Assessments • Abbreviation list • Section 9.5.1.4.2 • Section 9.5.1.5.12 • Table 6 • Table 7 |
| Prohibit concomitant medications that are strong CYP3A4, inhibitors, but clarify that no restrictions are needed for other CYP3A4 | At request of FDA, in light of finding that inhibition of CYP3A4 by a reference agent increases plasma levels of E2609 | 
 • Synopsis – 
 ○ Concomitant Drug/Therapy • Section 7.1 |

Revisions to Version 1.0

New version/date: Version 2.0, 21 Oct 2014 (revised original protocol)

| Change | Rationale | Affected Protocol Sections |
|--|---|---|
| inhibitors, CYP3A4 inducers, or CES2 inhibitors | | 
 • Section 9.4.7 • Appendix 2, Listing 6 |
| Addition of tests for viral characterization at Baseline | To confirm by serology information of subjects prior exposure to common viruses pre-dosing with study drug | 
 • Section 9.5.1.2.2 • Table 4 • Table 6 • Table 8 |
| Use of a centralized dermatologist assessment via photography | A centralized approach, using standardized photography, to FDA-required serial dermatological assessments will be employed for consistency of assessments between sites and for consistency of longitudinal assessments of individual subjects. | 
 • Synopsis – 
 ○ Safety Assessments • Section 9.2.5 • Section 9.5.1.5 • Section 9.5.1.5.8 • Table 6 • Table 7 |
| Removal of testing for benzodiazepines or opioids as part exclusion criteria #35 | To differentiate appropriate medicinal use from recreational drug use or abuse | 
 • Synopsis – 
 ○ Exclusion Criteria • Section 9.3.2 |
| Addition of analysis of other covariates such as adjusted hippocampal volume will be studied | Hippocampal volume has been shown to correlate with rate of cognitive decline and as such is a key covariate to be used in the analyses. | 
 • Synopsis – 
 ○ Analysis of Primary Endpoint • Section 9.7.1.6.1 |
| Addition of clarifications to ophthalmic examination | To provide more detail around the requirements for the ophthalmic exam | 
 • Synopsis – 
 ○ Safety Assessments • Section 9.5.1.5.13 • Table 6 • Table 7 |
| Addition of details regarding specific method of CSF collection (ie, gravity drip) | Use of materials required for suction method when collecting CSF can affect the PD data and so it is important to make it clear that only the gravity drip method can be used for collecting CSF in this study for protecting the quality and the consistency of the CSF PD data. | 
 • Section 9.5.1.3.3 • Section 9.5.1.4.2 • Table 6 • Table 7 |
| Addition of specific testing for B12 levels at Screening | Abnormally low serum vitamin B12 levels are exclusionary for the study (exclusion criterion 8) but a blood draw for Vitamin B12 was inadvertently missed out of Table 6 in protocol version 1. | 
 • Synopsis – 
 ○ Exclusion Criteria • Section 9.3.2 • Section 9.5.1.2.3 • Figure 2 • Table 6 |
| Addition of details regard AEs that might be signals of possible drug abuse potential | Changed terminology re: collection of additional information for AEs that might be signals of possible abuse potential. No longer use the | 
 • Synopsis – 
 ○ Safety Assessments • Section 9.2.5 • Section 9.5.1.5.1 |

Revisions to Version 1.0

New version/date: Version 2.0, 21 Oct 2014 (revised original protocol)

| Change | Rationale | Affected Protocol Sections |
|--|---|---|
| | word "narrative" in order to avoid potential confusion with standard clinical trial narratives eg, for serious adverse events, adverse events leading to withdrawal, etc. | 
 Appendix 4 |
| Addition of clarification regarding position for taking vital signs (ie, supine) | The American Heart Association guidelines only mention supine, standing, and sitting as positions for taking HR and BP measurements. Therefore, have changed required position from semi-supine to sitting. | 
 Section 9.5.1.5.4 Table 6 Table 7 |
| Stipulated that study drugs are to be taken with food | For consistency of treatment conditions | 
 Section 9.5.1.4.1 |
| Change to list of Study Specific AEs which should be considered SAEs | Eisai's standard procedures have changed such that non-serious study specific adverse events of interest are no longer reported to Eisai Product Safety; instead, any additional information required for such non-serious adverse events will be obtained through other methods. In addition, certain events (new onset seizures, ocular herpes) are now to be classified as serious as important medical events, regardless of whether they meet standard ICH serious criteria. | 
 Section 9.5.1.5.1 Section 9.5.1.5.2 |
| Increased blood volume for PK | To match collection tubes and ensure sufficient sample for planned assays | 
 Table 8 |
| Corrected error in definition of PK analysis set | For accuracy | 
 Synopsis – 
 Study Endpoints Section 9.7.1.2 |
| Addition of details regarding discontinuation of study drug | To clearly and consistently differentiate "discontinuation from study drug" from "withdrawal from study" | 
 Synopsis Section 7 Section 9.1.2.1 Section 9.2.5 Section 9.3.3 Table 1 Table 2 Section 9.4.1 Section 9.4.4 Section 9.5.1.5.1 Section 9.5.1.5.3 Section 9.5.5 |

Revisions to Version 1.0

New version/date: Version 2.0, 21 Oct 2014 (revised original protocol)

| Change | Rationale | Affected Protocol Sections |
|--|---|--|
| Re-ordered prohibited medication lists | For consistency, all lists re-ordered in alphabetical order of generic drug name, and footnotes revised for overall consistency | 
• Appendix 2 |
| Moved nefazodone from Listing 9 to Listing 6 | Nefazodone is a strong CYP3A4 inhibitor and is therefore prohibited. | 
• Appendix 2 |

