9.1.1 Prerandomization Phase

The Prerandomization Phase includes a Screening Visit and a Baseline Visit. All Screening Visit assessments must be completed and eligibility to progress must be confirmed before any Baseline Visit assessments are performed. All Screening Visit and Baseline Visit assessments must be completed within 50 days (plus an additional window of up to 30 days if required [revised per Amendment 02]) and a window of no more than 10 days is to be observed between the completion of all Baseline Visit assessments (including confirmation of eligibility following all Baseline Visit assessments) and randomization into the study at Visit 3 (revised per Amendment 02). Thus, the Prerandomization Phase will last for up to 60 days, plus an additional window of 30 days if required (revised per Amendment 02). The

series of assessments conducted during this phase will determine eligibility for randomization into the study.

Inclusion criteria are discussed in [Section 9.1](#) and detailed in [Section 9.3.1](#). Before randomization, the clinician will provide a judgment on the classification of a subject as either MCI/Prodromal or likely mild to moderate AD. (revised per Amendment 01) This judgment may be discussed and reviewed with the sponsor or sponsor's representative, as necessary.

Results of the Screening safety magnetic resonance imaging (MRI) will be valid for 90 days from the date of scanning. Results of the lumbar puncture (LP) from subjects who voluntarily consent for CSF measurement will be valid for 90 days from the date of testing. Results of Screening PET scans conducted specifically for this study and for use in the longitudinal analyses will also be valid for 90 days from the date of scanning. These assessments will not need to be repeated should the subject be randomized within that time period either under their original subject identification number or under a new re-screening subject identification number. Historical PET scans used for determination of eligibility only (ie, not used for the longitudinal analyses) are valid for 12 months. (revised per Amendment 02)

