9.1.2.3 Follow-Up Period

All subjects, regardless of whether they complete all 18 months of treatment or discontinue study drug prematurely, will complete 4 posttreatment Follow-up Visits: 2, 4, 8, and 12 weeks after the last dose of study drug. If clinically indicated, more frequent safety assessments can be conducted as part of Unscheduled (UNS) Visits during the posttreatment Follow-up Period. (revised per Amendment 04)

The end of the study will be defined as the date of the clinical database lock (ie, when all study data are collected and data validation is completed).

As required by some regulatory agencies, the following estimates are provided:

- The study will begin in Nov 2014 and is projected to end by Apr 2018. (revised per Amendment 05)
- The maximum estimated period for each subject on study is anticipated to be approximately 2 years.

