Appendix 6 Extension Phase

(revised per Amendments 07 and 08)

PRIMARY OBJECTIVE

- To assess the long-term safety and tolerability of daily dosing with elenbecestat 50 mg in mild cognitive impairment (MCI)/Prodromal subjects and in subjects with mild to moderate dementia due to Alzheimer's disease (AD)

SECONDARY OBJECTIVES

- To explore the long-term effects of elenbecestat on clinical status by assessment of:
 - a. The Mini-Mental State Examination (MMSE)
 - b. The Functional Assessment Questionnaire (FAQ; also known as the Functional Activities Questionnaire)
- To explore the long-term effects of elenbecestat on:
 - a. Volumetric magnetic resonance imaging (vMRI) including, but not limited to, total hippocampal volume, left and right hippocampal volume, whole brain volume, and total ventricular volume at 24 and 48 months of treatment in the Extension Phase.
 - b. Plasma amyloid at 12, 24, 36, and 48 months of treatment in the Extension Phase

ELIGIBILITY CRITERIA

Subjects who do not meet all of the inclusion criteria or who meet any of the exclusion criteria will not be eligible to receive study drug.

Inclusion:

1. Subjects who complete the 18-month treatment and the 12-week Follow-up Period (Visit 20) in the Core Study and whose Visit 20 falls within a 4-week window from the start of the Extension Phase (Visit 21). Permission must be obtained from the medical monitor if Visit 21 is to occur more than 4 weeks from Visit 20.
2. Subjects must continue to have an identified caregiver or informant who is willing and able to provide follow-up information on the subject throughout the course of the Extension Phase.

Exclusion:

1. Subjects who discontinue study drug prematurely during the Core Study are not eligible to participate in the Extension Phase.

2. Subjects with any active infection within 4 weeks of Visit 21
3. Subjects with absolute lymphocyte count below the Lower Limit of Normal (LLN) within 10 days of Visit 21
4. Subjects who develop the following conditions from the time of screening for the Core Study to the start of the Extension Phase:
 - a. Hepatic impairment, with total bilirubin greater than $1.5 \times$ upper limit of normal (ULN) or International Normalized Ratio (INR) greater than 1.7. Subjects with Gilbert's syndrome need not be excluded on the basis of an elevated bilirubin, provided that they have no other signs or symptoms suggestive of hepatic impairment

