Eligible subjects who choose to participate in the Extension Phase may enter the Extension Phase immediately following the completion of Visit 20 (ie, Visit 21 procedures may be completed on the same day as Visit 20). Subjects who are eligible to participate in the Extension Phase but who do not transition to the Extension Phase on the day of Visit 20 may enter the Extension Phase any time within 4 weeks of Visit 20. The medical monitor must be contacted if Visit 21 is to occur more than 4 weeks after Visit 20. For all subjects, assessments performed at Visit 20 may serve as baseline values for the Extension Phase (ie, results of assessments conducted at Visit 21) with exceptions of laboratory assessments and vital signs, which must be repeated if Visit 21 occurs more than 10 days from Visit 20.

During the Extension Phase, subjects will receive open-label elenbecestat 50 mg per day for up to 48 months. Subjects with pending INR and serum pregnancy test results (females subjects of childbearing potential only) but who are otherwise qualified may begin Extension Phase dosing at Visit 21; however, these subjects must discontinue study drug treatment immediately if either test result meet the exclusion criteria.

Safety assessments will be performed as described in [Table 14](#). Subjects may discontinue from study drug for any reason. Subjects who complete 48 months of the Extension Phase treatment or who discontinue the study drug must comply with the Early Discontinuation (ED) Visit (within 7 days after the last dose of study drug) and the Follow-up Visits (Weeks 4 and 12 after the last dose of study drug).

The study will end when the last visit for the last subject has completed the Extension Phase.

Removal of Subjects from Therapy or Assessment

The investigator may discontinue study drug or withdraw the subject from the study at any time for safety or administrative reasons. The subject may decide to stop study drug or withdraw from the study at any time for any reason. Subjects who discontinue study drug prematurely for any reason will undergo an ED Visit within 7 days of their last dose of study drug. Subjects who discontinue from treatment during the Extension Phase will have 2 posttreatment Follow-up Visits at 4 and 12 weeks after the last dose of study drug.

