 - e: Unscheduled visits may be conducted at any time that additional assessments, including MRI scans, are clinically indicated in the judgment of the investigator. Note that not all assessments indicated under UNS Visits need be conducted – actual assessments needed will be determined by the investigator and will be based on the specific visit needs.
 - f: Result from Visit 20 will also serve as Visit 21 result. If the specified assessment was not performed at Visit 20, it must be performed at Visit 21.
 - g: Dermatologic assessment by the investigator must be performed at Visit 21 in addition to the centralized skin assessment (using standardized photography) performed at Visit 20.
 - h: Only if clinically significant abnormalities are found at the Follow-up Week 4 Visit and the investigator considers it necessary to repeat at the Follow-up Week 12 Visit.
 - i: Measurements of body temperature and sitting blood pressure and sitting heart rate will be obtained.
 - j: Result from Visit 20 will also serve as Visit 21 result if Visit 21 occurs within 10 days from Visit 20. If Visit 21 occurs more than 10 days after Visit 20, the assessment must be repeated at Visit 21.
 - k: Examples of neurological signs that may indicate new central nervous system pathology that may need further investigation include (but not limited to) visual disturbance, dysarthria, dysphasia, muscle strength, limb weakness, hyperflexia, paraparesis, micturition difficulty or urgency or incontinence, ataxia, neuropsychiatric or cognitive decline in excess of expectations based on the subject’s recent history. The Brief Smell Identification Test (Sensonics Inc.) will be administered at the same visits and serves as part of the neurologic examination.
 - l: Please refer to [Section 9.4.7](#), which describes prohibited and permitted medications in the study.
 - m: Result from Visit 20 will also serve as Visit 21 result if Visit 21 occurs on the same day as Visit 20. If Visit 21 occurs more than 1 day after Visit 20, the assessment must be repeated at Visit 21.
 - n: Single 12-lead standard ECGs will be recorded. If the QTcF is greater than 450 msec, perform 2 more 12-lead standard ECGs 1 minute apart and take the mean of the 3 QTcF values.

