The following secondary efficacy endpoints will be summarized by descriptive statistics and/or graphs, using OLE-FAS:

- Changes from Core Study and Extension Phase baselines in MMSE and FAQ scores
- Changes from Core Study and Extension Phase baselines in vMRI parameters including, but not limited to, total hippocampal volume, left and right hippocampal volume, whole brain volume, and total ventricular volume at 24 and 48 months

The relationship between efficacy endpoints and biomarker endpoints will be explored using correlation analysis.

Pharmacodynamic Analyses

The OLE PD Analysis Set will be used for the summaries and analyses of PD biomarkers. The percentage change in plasma amyloid measurements from Core Study and Extension Phase baselines to 12, 24, 36, and 48 months of Extension Phase treatment will be analyzed and presented graphically.

SAMPLE SIZE RATIONALE

Subjects who complete the Core Study will have the option to participate in the Extension Phase. There is no sample size calculation for the Extension Phase.

PROTOCOL SIGNATURE PAGE

(revised per Amendment08)

Study Protocol Number: E2609-G000-202

Study Protocol Title: A Placebo-Controlled, Double-Blind, Parallel-Group, Randomized, Dose-Finding Study To Evaluate the Safety and Tolerability of Elenbecestat (E2609) in Subjects With Mild Cognitive Impairment due to Alzheimer’s Disease (Prodromal Alzheimer’s Disease) and Mild to Moderate Dementia Due to Alzheimer’s Disease (revised per Amendments 01 and 05)

Investigational Product Name: Elenbecestat (E2609)

IND Number: 109308

EudraCT Number: 2014-002723-94

SIGNATURES

Authors:

| | |
|--|---------------|
| _____ PPD [Redacted] Neurology Business Group, Eisai Ltd | _____ Date |
| _____ PPD [Redacted] Neurology Business Group, Eisai Inc. | _____ Date |
| _____ PPD [Redacted] Neurology Business Group, Eisai Inc. | _____ Date |
| _____ PPD [Redacted] Neurology Business Group, Eisai Inc. | _____ Date |

INVESTIGATOR SIGNATURE PAGE

Study Protocol Number: E2609-G000-202
Study Protocol Title: A Placebo-Controlled, Double-Blind, Parallel-Group, Randomized, Dose-Finding Study To Evaluate the Safety and Tolerability of Elenbecestat (E2609) in Subjects With Mild Cognitive Impairment due to Alzheimer's Disease (Prodromal Alzheimer's Disease) and Mild to Moderate Dementia Due to Alzheimer's Disease (revised per Amendments 01 and 05)
Investigational Product Name: Elenbecestat (E2609)
IND Number: 109308
EudraCT Number: 2014-002723-94

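### Visit 20 results can serve as Extension baseline at any age, so for late entrants change from Extension baseline in MMSE, FAQ and possibly vMRI includes off-drug decline

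*Protocol*

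**What the plan says.** Table 14, footnote f, states: "Result from Visit 20 will also serve as Visit 21 result. If the specified assessment was not performed at Visit 20", Visit 21 is where it has to be done. The footnote is attached to the Visit 21 entries for MMSE, FAQ, neurological examination, ECG, C-SSRS, safety MRI and vMRI, physical examination, weight, PD blood, PBMC and stored immune-status blood. The study design text of Appendix 6 likewise lets Visit 20 assessments stand as Extension baseline for all subjects, "with exceptions of laboratory assessments and vital signs, which must be repeated if Visit 21 occurs more than 10 days from Visit 20".

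Other items at the same visit do have limits. Footnote j gives laboratory tests and vital signs 10 days. Footnote m requires adverse events and concomitant medications to be redone if Visit 21 is more than 1 day after Visit 20. Footnote g requires an investigator dermatologic assessment at Visit 21. Footnote u asks for MRI within 7 days before Visit 21, but only where applicable.

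On timing of entry, Inclusion 1 of Appendix 6 says: "Permission must be obtained from the medical monitor if Visit 21 is to occur more than 4 weeks from Visit 20". The Synopsis (Study Design), Section 9.1.3, the Appendix 6 design text and Table 14 footnote b ask only that the monitor be contacted. None gives an upper limit or ties late entry to a repeat assessment.

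For Core entry, Section 9.1.1 states: "Results of the Screening safety magnetic resonance imaging (MRI) will be valid for 90 days from the date of scanning".

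**The concern.** Change from Extension Phase baseline in MMSE, FAQ and vMRI is a named secondary endpoint of the Extension. If the baseline value is months old, the change covers the untreated interval before Visit 21 as well as the open-label treatment. In a progressive disease this makes on-treatment worsening look larger. The distortion is concentrated in the earliest-enrolled subjects, because the Extension did not exist when they finished the Core Study.

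The same values also support entry decisions. Exclusion 6 (brain MRI findings) gives no date for the scan, and footnotes f and u point in different directions.

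**Working it through.** **Inputs (all Protocol).**
- Study start: "The study will begin in Nov 2014 and is projected to end by Apr 2018" (Section 9.1.2.3). This is given as an estimate, with no day, and is not stated to be a first dose.
- Prerandomization: up to 60 days, plus up to 30 more (Section 9.1.1).
- Treatment 78 weeks and follow-up 12 weeks (Section 9.1).
- Visit windows: Visit 18 ±10 days and follow-up visits ±3 days (Table 7 footnote a), so ±13 days together.
- Extension first added: Version 9.0, Amendment 07, 01 Feb 2017 (Revision History).

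**Reproducing the plan's figure.** Visit 20 day = 1 + 7 × (78 + 12) = 631, which matches Table 7.

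**Shortest gap for the earliest completers.** Gap = 01 Feb 2017 − (start date + prerandomization days + 630 days). Months are days / 30.4375.

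| Start | Prerandomization | Visit 20 | Gap to 01 Feb 2017 |
|---|---|---|---|
| 1 Nov 2014 | 0 days | 23 Jul 2016 | 193 days (6.3 months) |
| 30 Nov 2014 | 0 days | 21 Aug 2016 | 164 days (5.4 months) |
| 1 Nov 2014 | 60 days | 21 Sep 2016 | 133 days (4.4 months) |
| 30 Nov 2014 | 60 days | 20 Oct 2016 | 104 days (3.4 months) |
| 30 Nov 2014 | 90 days | 19 Nov 2016 | 74 days (2.4 months) |

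The visit windows widen the range to 74 − 13 = 61 days and 193 + 13 = 206 days, or 2.0 to 6.8 months. Ethics approval of the amendment (Section 5.1) adds an unstated amount.

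**Who is affected.** Cut-off for first dose = 01 Feb 2017 − gap − 630 days.
- Gap over 28 days: first dose before about 15 Apr 2015.
- Gap over 90 days: first dose before about 12 Feb 2015.
- Gap over 6 months (Visit 20 before 1 Aug 2016): first dose before about 10 Nov 2014, or 23 Nov 2014 if visits ran 13 days early.

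**Size of the distortion.** Month 24 of the Extension is 104 weeks, or 728 days. A gap of 61 to 206 days lengthens that interval by 61/728 = 8% to 206/728 = 28%.
- vMRI, if footnote f governs: Section 9.2.4.4 cites annual change of 2% to 3% in the AD brain and comparable rates in amyloid-positive MCI. The gap adds 2% × 61/365.25 = 0.3% to 3% × 206/365.25 = 1.7% of volume.
- MMSE: the protocol gives no rate of decline. Assuming 1 to 3 points per year, the gap adds 1 × 61/365.25 = 0.2 to 3 × 206/365.25 = 1.7 points.

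**The case against.** Several counter-arguments stand in whole or part.

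A reader might infer that early completers must enter more than six months late. The documents do not support that. Entry is optional: "Subjects who complete the Core Study will have the option to participate in the Extension Phase". A gap over six months arises only with a first dose in early to mid-November 2014 and almost no time for four-tier screening that includes MRI and PET.

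A reader might also infer that QTcF prolongation or suicidal ideation arising in the gap goes unscreened. That is mostly wrong. Table 7 footnote e makes ECG, C-SSRS and physical examination conditional at Visit 20. Where they were not done there, the second sentence of footnote f requires them at Visit 21. The Synopsis, Section 9.2.5 and Appendix 6 also place C-SSRS at Visit 21. Carry-over affects these items only in subjects who had them at Visit 20. Exclusions 4, 7, 10 and 11 give further cover up to entry.

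MRI is ambiguous rather than plainly unlimited, because of footnote u. PD blood has a similar conflict: Table 14 marks it with footnote f, but Table 13 footnote a can be read as applying the 10-day rule to every baseline blood sample.

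The endpoint harm is limited. The Extension is uncontrolled, these endpoints are summarized descriptively, and change from Core Study baseline is reported alongside and is untouched by footnote f. The derivation of baseline may also be settled in a statistical analysis plan not shown here. The protocol itself, however, says that Visit 20 values may serve as baseline for all subjects.

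Finally, Version 10.0 is dated 10 Dec 2018, after the projected Apr 2018 end, so most Visit 21s were probably complete by then. The analysis part of the fix is therefore the part most likely to matter.

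**Conclusion.** The point holds. Footnote f and the Appendix 6 design text set no maximum age for Visit 20 values used as Extension baseline, and the 4-week window has no ceiling and two differently worded controls. On the protocol's own dates, anyone first dosed before about mid-April 2015 could enter only outside that window. For the earliest completers the shortest gap to the amendment date is about 2 to 6.8 months, which lengthens the 24-month change interval by roughly 8% to 28%. The effect is firmest for MMSE and FAQ, which are routine at Visit 20 and have no competing rule. It is conditional for vMRI and PD blood, where the text conflicts.

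This rests on the Nov 2014 estimate being met and on some early completers having entered late; the number who did is not stated. The bias exaggerates on-treatment worsening. It affects descriptive secondary summaries, not the primary safety objective or the Core Study comparison.

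**What to change.** 1. **Baseline rule.** When Visit 21 is more than 4 weeks after Visit 20, collect MMSE, FAQ and PD blood at Visit 21, where Table 14 already schedules them, and use those values as Extension baseline. This costs two short scales and one 4 mL sample per late entrant.
2. **Subjects already entered late.** Report the Visit 20 to Visit 21 gap and summarize change from Extension baseline, vMRI included, separately for late entrants. This needs analysis wording only.
3. **Entry safety.** Reconcile Table 14 footnotes b, f, j and u, Inclusion 1 and Exclusions 5 to 7 on how old an MRI, ECG, C-SSRS or neurological result may be at entry. State whether late entry needs the medical monitor's permission or only contact. Align Table 13 footnote a with Table 14 for PD blood. The clinical rule is for the sponsor to set; none is proposed here.
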